## 2 ABBREVIATIONS AND DEFINITIONS

### 2.1 ABBREVIATIONS

**AKI** = Acute Kidney Injury

**COVID** = Coronavirus Disease

**CKRT** = Continuous Kidney Replacement Therapy

**CMO** = Comfort Measures Only

**CVVHDF** = Continuous Venovenous Hemodiafiltration

**CVVHD** = Continuous Venovenous Hemodialysis

**CVVH** = Continuous Venovenous Hemofiltration

**CVP** = Central Venous Pressure

**CPR** = Cardiopulmonary Resuscitation

**DSMB** = Data and Safety Monitoring Board

**DNR** = Do Not Resuscitate

**DNI** = Do Not Intubate

**ECMO** = Extracorporeal Membrane Oxygenation

**EMR** = Electronic Medical Records

**ESKD** = End Stage Kidney Disease

**FiO2** = Fraction of Inspired Oxygen

**FO** = Fluid Overload

**GCS** = Glasgow Coma Scale

**GRADE** = Grading of Recommendations Assessment, Development and Evaluation

**HR** = Heart Rate

**HRPO** = Human Research Protection Office

**ICU** = Intensive Care Unit

**IDH** = Intradialytic Hypotension

**IHD** = Intermittent Hemodialysis

**IBW** = Ideal Body Weight

**IRB** = Institutional Review Board

**ITT** = Intent to Treat

**KDIGO** = Kidney Disease Improving Global Outcomes

**LAR** = Legally Authorized Representative

**MAP** = Mean Arterial Pressure

**MBW** = Measured Body Weight

**NBAC** = National Bioethics Advisory Commission

**NIH** = National Institute of Health

**OHRP** = Office of Human Research Protection

**PaO2** = Partial pressure of arterial oxygen

**PBW** = Predicted Body Weight

**RENAL** = Randomized Evaluation of Normal versus Augmented Level of Kidney Replacement Therapy

**KRT** = Kidney Replacement Therapy

**SAEs** = Adverse events that are serious and unexpected and have a reasonable possibility that the event was due to a study procedure

**SBP** = Systolic Blood Pressure

**SCUF** = Slow Continuous Ultrafiltration

**SpO2** = Oxygen Saturation via pulse oximetry

**S/F** = SpO2/FiO2 ratio

**SUSAR** = Serious and Unanticipated Suspected Adverse Reactions

**SOFA** = Sequential Organ Failure Assessment

**SW-CRT** = Stepped-wedge Cluster Randomized Trial

**TPN** = Total Parenteral Nutrition

**UPMC** = University of Pittsburgh Medical Center

**UFNET** = Net Ultrafiltration

## 2.2 DEFINITIONS

**Adverse Event:** Any untoward medical occurrence associated with the use of a drug or a study procedure, whether or not considered related to the drug or study procedure.

**Adverse Reaction:** Any adverse event caused by a drug or a study procedure. An adverse reaction is a subset of all suspected adverse reactions where there is a reason to conclude that the drug or the study procedure caused the event.

**Continuous Kidney Replacement Therapy (CKRT):** A form of continuous dialysis frequently used to remove solutes and fluid in critically ill patients with acute kidney injury.

**Continuous Venovenous Hemodiafiltration (CVVHDF):** A modality of continuous dialysis in which solute clearance occurs by diffusion and convection.

**Continuous Venovenous Hemodialysis (CVVHD):** A modality of continuous dialysis in which solute clearance occurs only by diffusion.

**Continuous Venovenous Hemofiltration (CVVH):** A modality of continuous dialysis in which solute clearance occurs only by convection.

**Slow Continuous Ultrafiltration (SCUF):** A modality of continuous dialysis in which only fluid is removed without any solute clearance.

**Funding:** National Institutes of Health (National Institute of Diabetes and Digestive and Kidney Diseases).

**Intention to Treat (ITT):** All eligible and consented patients who undergo randomization will be included in the ITT cohort for the purposes of analyzing the primary and secondary study outcomes.

**Intravascular Volume:** The circulating volume of red cells and plasma within arteries and veins.

**Intermittent Hemodialysis:** A modality of dialysis done intermittently in which the solute clearance occurs by diffusion.

**Legal Representative:** An individual, judicial, or other body authorized under applicable law to consent on behalf of a prospective patient to the patient's participation in the clinical study.

**Net Ultrafiltration:** The net volume of fluid removed from the patient by the dialysis machine after discounting fluids administered (e.g., replacement fluids and dialysate given during CVVHDF) via the dialysis machine for the purpose of conducting the dialysis as well as fluids given to the patient (e.g., IV fluids, medications).

**Net Ultrafiltration Rate:** The rate at which the net ultrafiltration volume is removed from the patient adjusted for patient body weight and unit time (*i.e.*, milliliters/kilogram/hour). This is the rate of depletion of circulating intravascular volume in the patient by fluid removal.

**Stepped-Wedge Cluster Randomized Trial:** A clinical trial in which randomization occurs at the group level (*e.g.*, ICU) rather than the individual patient level. Each group then “crosses over” from control to intervention at a randomized time point and multiple “time steps” of data collection occur.

**Study Day:** The day of study enrollment is study day zero. The next day is study day one etc.

**Study Hospital:** Defined as the hospital where the patient was enrolled.

**Study ICU:** Defined as the study ICU in which patient was enrolled.

**Study Withdrawal:** Defined as permanent withdrawal from study before completion of study activities. This does not include those subjects who have completed the protocol procedures or stopped procedures because they have reached independence from CKRT. If a patient or surrogate requests withdrawal from the study the clinician will seek explicit permission to continue data collection.

**Suspected Adverse Reaction:** Any adverse event for which there is a reasonable possibility that the study procedures caused the adverse event. Reasonable possibility means there is evidence to suggest a causal relationship between the study procedures and the adverse event. A suspected adverse reaction implies less certainty about causality than an adverse reaction (21 CFR 312.32(a)).

**Ultrafiltration:** Ultrafiltration is the process by which plasma water devoid of cells and colloids is forced by hydrostatic pressure across an extracorporeal, biosynthetic, semipermeable, hemofiltration membrane, resulting in removal of patient intravascular volume.

### 3 EXECUTIVE SUMMARY

“Net ultrafiltration (UFNET),” also known as net fluid removal during kidney replacement therapy, has been used in the treatment of fluid overload among critically ill patients with acute kidney injury (AKI) for more than seven decades. However, the optimal rate of fluid removal (*i.e.*, UFNET rate) remains uncertain, complications such as hypotension and cardiac arrhythmias occur frequently, and more than 40% of patients die. Observational studies in critically ill patients receiving continuous kidney replacement therapy (CKRT) show that UFNET rate has a “J” shaped association with mortality with both slower and faster UFNET rates associated with increased risk of death compared with moderate UFNET rates.

Our long-term goal is to determine whether a restrictive UFNET rate strategy is associated with lower 90-day mortality compared with a liberal UFNET rate strategy in a multicenter, randomized, clinical trial in critically ill patients with AKI. The overall objective of this randomized trial is to establish the feasibility of maintaining patients in the restrictive UFNET rate strategy during treatment with CKRT. Our central hypothesis is that a restrictive UFNET rate strategy embracing a “slow and steady” approach to fluid removal is associated with fewer complications, including cardiac arrhythmias, hypotension, and death, compared with a more liberal “sprint and pause” strategy among critically ill patients.

We propose a prospective, two-center, unblinded, parallel-group, 2-arm, comparative effectiveness, stepped-wedge cluster-randomized trial among 112 critically ill patients with AKI treated with CKRT in 10 ICUs across two hospital systems. The trial will be conducted at 5 ICUs at University of Pittsburgh Medical Center in Pittsburgh, PA, as well as 5 ICUs at Mayo Clinic, Rochester, MN. ICUs will be randomized 1:1 to either a restrictive or a liberal UFNET rate strategy. During the first six months, all ICUs will continue with a liberal UFNET rate strategy. Thereafter, one ICU will be randomized to deploy the restrictive UFNET rate strategy using a rolling randomization strategy. In the liberal group, the UFNET rate will be titrated between 2.0-5.0 mL/kg/h and maintained throughout fluid removal. In the restrictive group, the UFNET rate will be titrated between 0.5-1.5 mL/kg/h and maintained throughout fluid removal. The UFNET rates used in both strategies are used in current clinical practice.

The primary feasibility outcomes are a.) between-group separation in mean delivered UFNET rates of a minimum of 0.53 mL/kg/h; b.) protocol deviation defined as UFNET rate out of range of >0.5 mL/kg/h lower or higher than the assigned UFNET rate range for six consecutive hours; and c.) patient recruitment of one patient per time window per ICU. We will explore the effects of restrictive and liberal UFNET rate groups on secondary outcomes such as daily and cumulative fluid balance, duration of kidney replacement therapy and mechanical ventilation, organ-failure free days, ICU and hospital length of stay, hospital mortality, and kidney replacement therapy dependence by hospital discharge.

We will also assess safety outcomes such as intradialytic hypotensive and hypertensive episodes; intradialytic cardiac arrhythmias; emergent use of rescue UFNET rates higher than the assigned group for treatment of fluid overload; severe hypophosphatemia, hypokalemia, and hypocalcemia; CKRT circuit downtime due to filter clotting or clogging; discontinuation of fluid removal due to hemodynamic instability; inability to close surgical wounds due to edema; new organ dysfunction; diastolic and systolic dysfunction; pulmonary edema; ileus, bowel ischemia, anastomotic break down; pressure ulceration; wound infections; arterial or venous thrombosis; severe anemia requiring red cell transfusion, severe thrombocytopenia requiring platelet transfusions; and secondary infections.

This feasibility trial will be used to support the rationale and design of a future multicenter phase III randomized trial to examine the effects of alternative UFNET rate strategies on patient-centered clinical outcomes.

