## 6 STUDY POPULATION AND ENROLLMENT

### 6.1 SETTING

The trial will accrue a maximum of 112 patients. Participants will be enrolled from 5 ICUs at the UPMC, Pittsburgh, PA, and 5 ICUs at the Mayo Clinic, Rochester, MN. At the UPMC, we will include the Transplant ICU, Medical ICU, and the Surgical Trauma ICU at the Presbyterian hospital, and the Medical-surgical ICU and Neuro-ICU (ICU8) at the Mercy hospital. At Mayo Clinic, we will enroll at the Medical-surgical ICU from the Methodist campus, and the Cardiac, Medical, Surgical, and CV Surgery ICUs at St. Mary's campus. No study ICU has a protocolized approach to fluid removal, and instead, clinicians determine the timing and rate of UFNET. All ICUs use specialized ICU nurses trained and certified in delivering CKRT. We expect each ICU to recruit one or more subjects per time window based on annual volume and past enrollment, allowing complete enrollment in 2.0 years.

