### 6.3.2 RANDOMIZATION UNIT

Following best practice recommendations for evaluation of system-level interventions, the unit of randomization is the cluster (*e.g.*, ICU) rather than the individual patient. During the first six months of data collection, all sites will continue with a liberal UFNET rate strategy. Thereafter, one ICU will be randomized to deploy the restrictive UFNET rate strategy every two months or when a maximum of 10 patients have been enrolled, whichever occurs first, and stay in this strategy until the end of the study (Figure 6).

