**Figure 6: Stepped-wedge cluster-randomized trial design**

We will use a computer-generated randomization scheme to determine the order in which each ICU would cross over from the liberal group to the restrictive group, with new crossover occurring every two months or whenever 10 patients have been enrolled, whichever occurs first. This trial design will allow us to stagger the implementation of the restrictive UFNET strategy while maintaining concurrent control over data collection in the ICUs that were not yet using the restrictive UFNET strategy.

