## 4 DATA ANALYSIS PLAN

### 4.1 OVERALL ANALYTICAL PLAN

All analyses will be performed on an intention-to-treat basis, which generally biases toward no difference. We will also perform per-protocol analyses where the assigned intervention was followed. We will first examine the data structure, distributions of the outcomes and explanatory variables, and potential missing data elements. Missing data will be imputed after examining the reason for missingness. For data that are missing completely at random or missing related to other collected covariates, we will use the multivariable imputation by chained equation (MICE) to impute data before fitting models.

The individual ICU is the unit of randomization, and the individual patient is the unit of analysis. In SW-CRT, the usual comparisons between two treatments need to be made over a differing time making standard group comparison-based methods biased and potentially ineffective. Therefore, we will use adjusted generalized linear mixed models (GLMM) for all primary and secondary outcomes, as delineated by Hussey and Hughes and others, to account for temporal and clustering effects typically encountered in SW-CRT designs. In these models, we will use the ICU as random effects. Time will be treated as random in the main analysis but will also be treated as fixed effects and interact with other covariates.

We will adjust all analyses for prespecified variables such as age, baseline eGFR, severity of illness as measured by the acute physiology and chronic health evaluation (APACHE)-III score, Elixhauser Comorbidity Index score, use or nonuse of mechanical ventilation, admission source, percentage of fluid overload before study enrollment, presence or absence of sepsis, baseline cardiovascular SOFA score and any other variable that are associated with outcome of  $UF_{NET}$  and had a between-group difference ( $P \leq 0.2$ ) on univariable analysis. We will assess the stability of final models using routine model diagnostics to identify potential outliers and/or influential observations. We will report both

adjusted and unadjusted analyses stratified by restrictive and liberal UFNET groups.

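### No center restriction on the ICU crossover order is stated and the model has no center term; pairing the order by center and adding one fixed effect would remove an avoidable source of error

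*Protocol*

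**What the plan says.** Protocol 6.1: "Participants will be enrolled from 5 ICUs at the UPMC, Pittsburgh, PA, and 5 ICUs at the Mayo Clinic, Rochester, MN".

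The text under Protocol Figure 6 (section 6.3.2) says: "We will use a computer-generated randomization scheme to determine the order in which each ICU would cross over", "with new crossover occurring every two months or whenever 10 patients have been enrolled, whichever occurs first". Section 6.3.2 sets an all-liberal lead-in: "During the first six months of data collection, all sites will continue with a liberal" rate strategy. The Executive Summary describes the restrictive "rate strategy using a rolling randomization strategy". None of these places mentions stratifying, pairing or otherwise restricting the order by center. Figure 6 is not reproduced in the text available.

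SAP 4.1 specifies generalized linear mixed models: "In these models, we will use the ICU as random effects". Time is random in the main analysis and fixed as an alternative. The named covariates are patient-level, and an open rule adds variables that are related to outcome and differ between groups at P ≤ 0.2. Center is not named there, nor in the adjustment footnotes to SAP shell Tables 2 and 3. The SAP still describes six ICUs, three per center.

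**The concern.** With only ten clusters in two centers, a single unrestricted list can send most of one center's ICUs across early. Restrictive data then come disproportionately from that center for much of the trial. If the two systems deliver different rates, part of that difference enters the estimated separation: it shrinks the separation if the higher-rate center crosses first and inflates it if that center crosses last.

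Separation in delivered rate is the first primary outcome, and Protocol 5.8.1 uses it to judge whether a larger study is feasible. The trial will run one realized order.

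**Working it through.** **Inputs.** From the protocol: 10 ICUs, 5 per center; one crossing per 2-month window after a 6-month lead-in (three windows); 24 months, so 12 windows; 0.93 patients per ICU per window; SD 0.75; ICC 0.01 or 0.1 (Table 6); target 0.53. Assumed: the center gap, since no document gives one.

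**1. The plan's own figure.** The Hussey–Hughes variance with one baseline period and ten steps (11 periods), N = 111 and ICC 0.01 gives SE 0.187. Power = Φ(0.53/0.187 − 1.96) = Φ(0.87) = 81%, and 109 patients are needed for 80%. The stated 111 is reproduced. The schedule as written (three lead-in windows, 12 in all) gives SE 0.195 and power 77.5%. That is a separate matter, but it is the layout used below.

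**2. Chance of a bunched order.** There are C(10,5) = 252 center placements. All five early crossings come from one center in 2; exactly four of five in 2 × 5 × 5 = 50. So 52/252 = 20.6%, and for all five, 2/252 = 0.8%.

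**3. A gap and an ICC that agree.** A gap of 0.5 split over 5 + 5 ICUs is a between-ICU variance of 0.25² = 0.0625. Against 0.75² = 0.5625 this is an ICC of 0.11. Conversely, ICC 0.01 means a between-ICU SD of √0.01 × 0.75 = 0.075, so the largest compatible gap is about 2 × 0.075 = 0.15.

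**4. Shift in the estimate.** With fixed periods and a random ICU intercept, each ICU's windows have covariance V = (1 − ICC)(0.75²/0.93)I + ICC(0.75²)J. The generalized least squares estimate is a weighted sum of cell means. A gap δ shifts it by δ times the summed weights of one center's ICUs. Over all 252 placements the mean shift is 0, and:

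| Gap, ICC | SD of shift | 95th percentile | Maximum | SE |
|---|---|---|---|---|
| 0.5, 0.11 | 0.08 | 0.16 | 0.21 | 0.21 |
| 0.15, 0.01 | 0.04 | 0.08 | 0.11 | 0.195 |

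The maximum in the second row is 0.15 × 0.71, where 0.71 is the maximum per unit gap at ICC 0.01. Shifts scale with the gap at a given ICC. With crossings paired by center, the SD at a 0.5 gap and ICC 0.1 falls to about 0.02. With a center term the shift is 0. A center difference in drift of 0.5 over 24 months (also assumed) gives SD about 0.07 at ICC 0.1, and about 0.02 when paired.

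**5. Simulation with the ICU variance estimated.** REML, fixed time, 111 patients, gap added to ICU variation at ICC 0.01, test of zero difference. There were 1,500 runs for random-order type I error and 800 for the rest, so the Monte Carlo error on power is about √(0.75 × 0.25/800) = 1.5 points.

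| Gap | Type I error, random order, no term | Power at 0.53, no term | Power at 0.53, with term | Bias, most unbalanced order, no term | Type I error, that order, no term |
|---|---|---|---|---|---|
| 0 | 5.5% | 76% | 75% | 0 | 6% |
| 0.25 | 5.9% | 73% | 75% | 0.16 | 15% |
| 0.50 | 5.3% | 71% | 76% | 0.24 | 25% |
| 0.75 | 7.3% | 64% | 77% | 0.24 | 23% |

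Over random orders bias is about 0 in every row. In the most unbalanced order a center term brings bias to about 0 and type I error to 4–7%. The simulated 0.24 slightly exceeds the 0.21 in step 4 because the fitted ICC in that order averaged 0.086, below 0.11.

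**The case against.** **Own control.** Protocol 6.3.1 relies on each ICU serving as its own control, and ICU is nested in center, so the ICU effect already takes up much of a constant gap. This stands as far as it goes. With about 11 patients per ICU the absorption is partial, as step 4 shows.

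**Random order.** A reader might infer that center differences are systematically taken for separation, or that the confidence interval is generally wrong. Neither is supported. Bias averages to zero, type I error averaged over orders stays near 5–7%, and the 15–25% rates belong to an order with probability 0.8%.

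**Larger shifts.** Combining a 0.5 gap with the planning ICC of 0.01 gives an SD of 0.14 and a 95th percentile of 0.27. Those inputs contradict each other (step 3), so those figures should not be used.

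**Evidence of a gap.** Protocol 6.1 says no study ICU has a protocolized approach. A reader might take this as evidence that the centers differ, but it describes something they share. During the trial both use the same rate ranges, rate calculator and standardized training. The gap remains an assumption.

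**Random time.** The calculation uses fixed periods, while the SAP's main analysis has time random. At ICC 0.01, with an assumed time variance of 0.005–0.05, the maximum leakage per unit gap falls from 0.71 to 0.42–0.51. It is smaller but not zero.

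**Silence.** The protocol does not say the order is unrestricted, and Figure 6 or the randomization program might contain a restriction. The P ≤ 0.2 rule might also admit center. Neither is stated, and a data-driven rule is a weak substitute for prespecifying a design factor.

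**Conclusion.** The point holds in a limited form. No center restriction on the order is stated and no center term is specified. The exposure is bias conditional on an unlucky order, plus some average loss of power. At an assumed gap of 0.5 mL/kg/h the shift has SD about 0.08 and can reach 0.21, against a 0.53 target; simulated power is 71% without the term and 76% with it. At a gap of 0.15, about the most that ICC 0.01 allows, the SD is 0.04, which is minor beside an SE of 0.195.

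These sizes rest on the assumed gap, fixed period effects and the 12-window schedule. They do not show that the primary analysis is invalid. This is a cheap improvement.

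**What to change.** 1. State in Protocol 6.3.2 whether the order is restricted by center. If it is not, generate it so that each consecutive pair of crossings contains one UPMC and one Mayo ICU, random within pair and within center. If the trial has begun, apply this to the ICUs not yet crossed.
2. In SAP 4.1, add center as a fixed effect to the primary and secondary models. This remains useful whatever order has been run.
3. Add a center-by-time term as a sensitivity analysis, because a constant center effect does not fully remove center-specific drift.
4. Make these edits when the SAP is updated from six to ten ICUs.

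Cost: one degree of freedom. With an unrestricted order the mean SE rises from 0.207 to 0.210 at ICC 0.11. With pairing plus the term, power at ICC 0.01 is 77.4% against 77.5% without either, so the sample size need not change on this account. Pairing makes the center, but not the ICU, of every second crossing predictable.

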## 4 TRIAL SUMMARY

**Title:** REstrictive versus Liberal rate of Extracorporeal Volume removal Evaluation in Acute Kidney Injury (RELIEVE-AKI) – a comparative-effectiveness, stepped-wedge cluster-randomized feasibility trial.

**Objective:** To evaluate the feasibility of alternative  $UF_{NET}$  rate strategies among critically ill adults with AKI and treated with CKRT.

**Study Design:** Two-center, prospective, unblinded, parallel-group, 2-arm, comparative effectiveness, stepped-wedge cluster-randomized trial (SW-CRT) of two  $UF_{NET}$  rate strategies conducted across 10 ICUs.

1. We will emphasize early screening and protocol initiation and enroll a maximum of 112 patients with AKI (KDIGO stage 3) who are treated with CKRT.
2. We will assess attending physician's equipoise twice daily as to whether fluid should be removed emergently or deferred.
3. We will emphasize safety by initiating  $UF_{NET}$  only when fluid removal is indicated as determined by the attending physician.
4.  $UF_{NET}$  rate will be calculated based on predicted body weight (PBW) to avoid confounding of actual weight by fluid overload.
5. Study protocol will be continued until the end of  $UF_{NET}$  while on CKRT.
6. We will allow enrollment of patients initiated on net fluid removal for less than 48 hours.
7. We will emphasize that the final decision to set and titrate  $UF_{NET}$  rate is at the discretion of the treating clinician.
8. We will allow not removing fluid per study protocol when the goal is to maintain patient in euvoolemia.
  
9. Restrictive  $UF_{NET}$  rate strategy
  - a.  $UF_{NET}$  rate will be initiated at 0.5 mL/kg/h of patient PBW.
  - b.  $UF_{NET}$  rate will be gradually increased 0.5 mL/kg/h as tolerated to maintain between 0.5-1.5 mL/kg/h throughout the study period.
  - c. We will recommend rescue intervention with faster  $UF_{NET}$  rates beyond 1.5 mL/kg/h only for emergent treatment of respiratory distress or severe hypoxia due to fluid overload.
  
10. Liberal  $UF_{NET}$  rate strategy
  - a.  $UF_{NET}$  rate will be initiated at 0.5 mL/kg/h of patient PBW.
  - b.  $UF_{NET}$  rate will be gradually increased 0.5 mL/kg/h as tolerated to maintain between 2.0-5.0 mL/kg/h throughout the study period.
  - c. We will emphasize safety by stipulating a maximum  $UF_{NET}$  rate of 5.0 mL/kg/h.
  - d. We will recommend rescue intervention with faster  $UF_{NET}$  rates beyond 5.0 mL/kg/h only for emergent treatment of respiratory distress or severe hypoxia due to fluid overload.

